## COGNITIVE SUBSTUDY

Newly enrolled participants at UW/UCD sites will have the option to enroll in the cognitive substudy, which per the Timeline table above, will include cognitive assessments at current study visits (baseline, 16 weeks and 28 weeks) and a new 48 week visit which will include cognitive assessment, blood draw, and psychological mechanisms of adherence measures (which includes text messaging surveys and traditional paper pencil questionnaires). Further detail below. All enrolled UAB site participants will receive these assessments.

**Cognitive Function** will be assessed using a gold-standard battery from the National Alzheimer's Coordinating Center (NACC) Universal Data Set (UDS), which balances participant burden with acquiring a comprehensive assessment. The assessment will be conducted by staff who are blind to intervention group. Staff will be trained and certified by the study PI and will be supervised weekly via meetings and communication. 30% of batteries will undergo double scoring by another staff member and 10% of batteries will be triple scored by the study PI. The PI will also observe assessments quarterly (either in person or video).

We will examine several outcomes, including continuous composites (corrected and uncorrected for demographics) across each domain, as well as a global cognitive functioning composite. We will also examine self-reported cognitive symptoms and declines in daily function. Finally, we will use cognitive T scores and subjective symptoms and everyday functioning declines to generate cognitive diagnoses. Though there are many approaches to operationalizing cognitive impairment in HIV, and in MCI, exist, we will employ validated approaches that are consistently used in neuroAIDS. Despite subtle differences in definitions, most include mild impairment in cognitive function (e.g., ~1 SD below mean on 2 tests/domains), and evidence of either subjective cognitive deficits or declines in daily function.

| One-hour Neurocognitive Assessment Battery |  |
|--|--|
| Domain                                     | Measure  |
| Depression and Everyday Functioning        | Depression: Patient Health Questionnaire 9-item Depression; Everyday Function & Cognitive Symptoms: Functional Activities Questionnaire, Cognitive Failures Questionnaire;   |

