will examine potential group (and site) differences in demographics and health and baseline measures with two-sample t test (or Wilcoxon), ANOVA (or Kruskal-Wallis test) or Chi-square test where appropriate. Variables that differ by group will be adjusted in sensitivity analyses. We will conduct primary analyses under an intention-to-treat principle (all participants analyzed based on randomized conditions). The impact of any missing data will be mitigated by the use of mixed effects modeling with baseline covariates that are conceptually relevant and associated to consistency in data collection. In the presence of missing data, mixed effects models are fitted with all available data and provide unbiased estimates of model parameters, as long as the data are missing at random or conditionally at random (conditional on the covariates). If appropriate, we will employ imputation techniques. False discovery rate (FDR) will be used to justify multiple comparison. All tests will be two sided.

Our primary aim is to determine the efficacy of HIIT vs CME on improving cognitive function over time. In stage 1 (baseline to 4 months), a general linear mixed model with participant ID as random effect:  $\text{score} = \text{Group} + \text{Time} + \text{Group} \times \text{Time} + \text{Site}$  will be used first to examine whether there is a significant group difference, wherein the study site is controlled to adjust for potential site effects. The best model fit with Bayesian information criterion (BIC) will determine the variance-covariance structure in above model. The significant interaction term in above model indicates a significant difference between two trajectories/slopes, i.e., treatment effect. The group comparison on the mean changes will also be contrasted with t test for effect size. In stage 2 (4 to 7 months), a similar general linear mixed model will applied:  $\text{score} = \text{Group1 (HIIT vs CME)} + \text{Group2 (Coaching vs Control)} + \text{Group1} \times \text{Group2} + \text{Time} + \text{Group1} \times \text{Time} + \text{Group2} \times \text{Time} + \text{Group1} \times \text{Group2} \times \text{Time} + \text{Site}$ , where the time is from 4 to 7 months. The non-significant interaction terms will be removed from the final model. Given any potential group differences in demographics and health at baseline, a sensitivity analysis will be conducted including those unbalanced variables in above models.

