For exploratory analysis, sex-by-group interaction and/or race-by-group interaction will be included in above models to explore the potentially moderating effects, conducted according to the rigorous methods proposed by Hayes. Given significant treatment effects on cognitive function, a PATH analysis will be conducted to explore the potential mediation effects of biomarker changes on cognitive function. We will also examine whether changes in parent R01 outcomes (e.g., VO2, physical function, fatigue) mediate cognitive changes. The exploratory blood markers will be obtained at baseline, 4- and 12 months, while the MRI neuroimaging markers will be obtained at the UAB site at baseline and 4 months. The group difference of biomarkers will be evaluated using a similar linear mixed regression model:  $\text{scores} = \text{Group} + \text{Time} + \text{Group} \times \text{Time}$ , where the group difference on slopes and mean changes will be contrasted.

Our secondary aim is to examine psychological MoA of adherence to habitual PA at 12 months. We will examine distal predictors (i.e., sociodemographics, physical health, intervention type [HIIT vs CME and coaching vs control], changes in parent R01 outcomes [e.g., weight loss, physical function, fatigue] using laboratory and survey data, and proximal psychological predictors using EMA (e.g., self-efficacy, perceived benefits, motivation, social support). First, we will use a linear mixed regression with random intercept:  $\text{PA} = \text{Predictor} + \text{Time} + \text{Predictor} \times \text{Time} + \text{Site}$ , to examine the association between PA adherence and each of the predictors of interest, adjusting for study site. Secondly, we will conduct a multiple linear mixed regression with random intercept and all significant predictors detected above as fixed effects to examine the covariate-adjusted association between PA and predictors:  $\text{PA} = \text{Time} + \text{Predictor1} + \text{Predictor2} + \dots + \text{Site}$ . The time-by-predictor interactions will be evaluated and removed from the model if not significant. The variance-covariance structure (e.g., AR1) in above models will be determined by the best model fit measured by Bayesian information criterion (BIC).

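### The stage-2 cognitive model lets the treatment-by-time terms be removed when non-significant; the main effects left behind do not estimate the month-4-to-7 effects

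*Combined protocol and SAP*

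**What the plan says.** The Cognitive Substudy Statistical Analysis (section IV.F) has two stages.

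- **Stage 1** (baseline to 4 months) uses "a general linear mixed model with participant ID as random effect", with group, time, their interaction and site. It is read as follows: "The significant interaction term in above model indicates a significant difference between two trajectories/slopes, i.e., treatment effect". The covariance structure is left to the data: "The best model fit with Bayesian information criterion (BIC) will determine the variance-covariance structure in above model".
- **Stage 2** is introduced with the words "a similar general linear mixed model will applied". It contains Group1 (HIIT vs CME), Group2 (coaching vs control), time, all two-way and three-way interactions among them, and site, "where the time is from 4 to 7 months". The next sentence is the removal rule: "The non-significant interaction terms will be removed from the final model". It names no exception and gives no significance threshold.

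The Cognitive Substudy section fixes the visits: the substudy "will include cognitive assessments at current study visits (baseline, 16 weeks and 28 weeks) and a new 48 week visit". Weeks 16 and 28 are the only visits in the stage-2 window. Under Aim 3, Randomization, coaching is allocated 1:1 once the exercise phase is over. The stage-2 model has no covariate for the month-4 score, and the plan does not say which coefficient is to be read as the stage-2 effect once terms have been removed.

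**The concern.** The plan identifies treatment effect with group-by-time, then lets that term be deleted when it misses significance. In a two-visit model whose first visit precedes coaching, the main effect is a different quantity. It mixes a visit at which coaching cannot yet have acted with one at which it can. For the exercise factor, both visits follow the supervised phase, so the main effect picks up whatever difference that phase left behind.

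At stake is the estimate and interval in the final model. A non-significant interaction is the case in which a reader most needs the size and precision of the month-4-to-7 effect, and there the rule removes the term that carries them.

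**Working it through.** The documents give no effect size, power or correlation for the stage-2 cognitive model, so there is no planned figure to reproduce.

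**Inputs**
- Visits in stage 2: months 4 and 7 (Cognitive Substudy; stage-2 model text).
- Expected coaching difference at month 4: d4 = 0, by randomisation after week 16.
- Substudy size: 110 (Study Timeline).
- Dropout 20%, alpha 0.05, correlations 0.5 and 0.7: stated in the Sample Size Calculations for the parent aims, borrowed here as assumptions. Correlation 0.85 is added as an assumption for cognitive scores.
- Per coaching arm: 110 × 0.8 / 2 = 44.
- Coaching effect at month 7: 0.30 SD, an assumption.

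**1. What Group2 estimates after removal.** Let s4² and s7² be the variances, c the covariance, and d4, d7 the arm differences at the two visits. The common-difference estimate is (1 − w)·d4 + w·d7, with

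w = (s4² − c) / (s4² + s7² − 2c).

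A random intercept with equal variances gives w = 1/2. With d4 = 0 the coefficient is d7/2: a true 0.30 SD becomes 0.15 SD.

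**2. Loss at month 7.** With a fraction q missing at month 7, equal variances and correlation ρ,

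w = (1 − q) / [2(1 − q) + q(1 + ρ)].

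| q | ρ = 0.5 | ρ = 0.7 | ρ = 0.85 |
|---|---|---|---|
| 0 | 0.500 | 0.500 | 0.500 |
| 0.10 | 0.462 | 0.457 | 0.453 |
| 0.20 | 0.421 | 0.412 | 0.406 |

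**3. Unequal variances, if BIC selects them.** At ρ = 0.7 with s4 = 1:
- s7 = 1.2, c = 0.84: w = 0.16/0.76 = 0.21.
- s7 = 0.8, c = 0.56: w = 0.44/0.52 = 0.85.

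The fraction can move either way.

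**4. What Group1 estimates after removal.** If the month-4 HIIT–CME difference D simply persists, d4 = d7 = D. The coefficient is then D for any w, while the stage-2 change is d7 − d4 = 0.

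**5. Check by fitted mixed models.** In 100 simulated trials (n = 88, ρ = 0.7), the truth was 0.30 SD for coaching at month 7 and a 0.50 SD exercise difference that persists unchanged.

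| Model | Coaching | Exercise |
|---|---|---|
| Main effects only | 0.17 | 0.49 |
| Group-by-time terms kept | 0.33 | 0.00 |

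The coaching ratio, 0.167/0.331, is 0.50.

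**6. How often removal occurs.** The SD of change is √[2(1 − ρ)] and the standard error of the coaching contrast is that SD × √(2/44).

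| ρ | SD of change | SE | 0.30/SE | Power | Removed |
|---|---|---|---|---|---|
| 0.5 | 1.000 | 0.213 | 1.41 | 29% | 71% |
| 0.7 | 0.775 | 0.165 | 1.82 | 44% | 56% |
| 0.85 | 0.548 | 0.117 | 2.57 | 73% | 27% |

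**7. Estimates after test-then-drop** (4,000 simulated trials per setting, n = 88).
- Coaching, true 0.30 SD, ρ = 0.7: the mean Group2 coefficient was 0.15 when the interaction was dropped. The mean interaction estimate was 0.45 when it was kept.
- Exercise, 0.50 SD difference persisting with no stage-2 change: Group1 × Time was dropped in about 95% of trials. The Group1 main effect was then significant in 66–72% (ρ = 0.85 and 0.7).

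**The case against.** A reader might infer that the plan will report a halved coaching effect and present stage-1 carry-over as a stage-2 exercise effect. The documents do not say so. Nowhere is a leftover main effect named as the stage-2 result, and on the plan's own definition a removed interaction could simply be read as no treatment effect detected. The interaction test in the full model is unbiased. The Group1 coefficient is also a legitimate estimate of a persisting difference if it is labelled as one. All of this stands. What remains is that, unless another coaching interaction survives, Group2 is the only coaching term in the final model, and nothing prevents it from being read as the coaching effect.

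The stage-1 text also adds a t-test contrast of mean changes to obtain an effect size. Applied to months 4 and 7, it would be untouched by term removal. That mitigation is partial, because the sentence belongs to stage 1 and is not repeated for stage 2.

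The scope is narrow. The substudy's primary aim is HIIT vs CME on cognition, and the stage-1 model carries no removal rule. No stated substudy aim tests coaching on cognition, which is itself on the parent protocol's exploratory outcome list.

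A reader might extend the argument to the 12-month physical-activity models, where "The time-by-predictor interactions will be evaluated and removed from the model if not significant". Those models examine associations with predictors. Their time interactions are not defined as treatment effects, and the derivation above does not carry over to them. Nor do the documents support a general statement that the substudy is underpowered, since they give no power figure for it.

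**Conclusion.** The concern holds for the stage-2 cognitive model only. If Group2 × Time is removed and the Group2 coefficient is read as the coaching effect, it estimates about half the month-7 effect. The fraction is exactly one half with two visits, complete data and equal variances, about 0.41 to 0.46 with 10–20% loss at month 7, and other values if BIC selects unequal variances. The leftover Group1 coefficient mainly reflects the stage-1 difference rather than change after month 4.

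The 71% to 27% removal frequency rests on the assumed 0.30 SD effect, 44 per arm, the 0.05 threshold and correlation 0.5 to 0.85. It also treats Group2 × Time as a test of the coaching contrast averaged over exercise arms. The halving result does not depend on the assumed effect size.

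The full-model test, the stage-1 cognitive comparison and the parent trial's outcomes are unaffected. The defect lies in the final-model estimate and interval, and in the lack of a specified effect size and interval for a non-significant treatment term. It should be corrected, but it does not threaten the trial's main conclusions.

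**What to change.** Replace the removal sentence for stage 2 with a statement along these lines:

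- Group1 × Time and Group2 × Time stay in the model whatever their p-values.
- The month-4-to-7 change contrasts for coaching vs control and for HIIT vs CME are reported with 95% confidence intervals, each averaged over the other factor if the three-way term is in the model.
- Any removal is limited to the three-way term (Group1 × Group2 × Time), by a rule stated in advance with its threshold.

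A model of the month-7 score adjusted for the month-4 score may be used for the coaching comparison. It should not be used for HIIT vs CME, because the month-4 score is itself affected by exercise arm. With equal variances its Group1 coefficient is d7 − ρ·d4. For a 0.30 SD difference that persists with no stage-2 change, that is 0.30 − 0.7 × 0.30 = 0.09 SD at ρ = 0.7, and 0.15 SD at ρ = 0.5, where the change contrast gives zero.

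The cost is a few lines in the analysis plan and a few degrees of freedom. No new data are needed.

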## F. Data Analysis Plan:

**Statistical Considerations.** We hypothesize that among older PWH, HIIT will lead to better physical function and reduced fatigue through improvements in mitochondrial bioenergetics compared with CME.

**Sample Size Calculations:** We assume a 1:1 randomization to HIIT or CME balanced by site, sex ( $\geq 25\%$  women) and age category (50-59, 60-69, and 70+) with a conservative 20% dropout rate, resulting in 40 evaluable participants/group. The second randomization at week 16 and will also be balanced by initial randomization (2x2 factorial design). Aim 1 and 2 power calculations assume two-sided, 2-sample/paired *t*-tests for between/within group comparisons of the change from baseline with a 0.05 significance level. We assume conservative within subject correlations ( $\rho$ ) of 0.7 or 0.5 to estimate the standard deviation (SD) of the outcome change, larger correlations and repeated measures will result in additional power. The Aim 1 primary outcome is change in 400-MWT. We assume an effect size comparable to Toohey, an intervention comparing HIIT to CME among middle-aged (mean age 51, SD 12 years) cancer survivors that resulted in a mean (SD) difference of 97 (82) and 36 (68) meters in 6-minute walk distance among HIIT and CME, respectively. Using  $\rho=0.7$ , and a sample size of 40/group, we will have  $>88\%$  power to detect a comparable *between* group differences of 45 (38) and 20 (38) second improvement in 400-MWT in HIIT and CME, respectively. For reference, in our prior exercise study, PWH had a 25 second improvement in 400-MWT. This also provides  $>99\%$  and  $>81\%$  power to detect *within* group differences in the HIIT and CME arms. For morning and evening fatigue, we assume a baseline mean of 19(8) and 27(8) points, respectively ([name], unpublished data). With  $\rho=0.5$ , and a sample size of 40/group, we will have  $>80\%$  to detect a change of  $\geq 27\%$  and  $\geq 20\%$ , respectively. The primary Aim 2 outcome is change in State 3 respiration. Based on Robinson, we estimate a baseline mean (SD) of 580 (180) pmol  $O_2$ /min/mL using  $\rho=0.5$ . This provides  $>81\%$  power to detect a difference in the change of 50% (HIIT) and 30% (CME). The muscle substudy is considered exploratory, however, we anticipate adequate power. Using preliminary data, combining HEALTH+ exercise groups (N=24), provides  $>80\%$  power to detect a change of -8.7% in MRI-PDFF of HEALTH+ participants. For within exercise group (CME or HIIT) comparisons, a sample size of 12 provides  $>80\%$  power to detect a difference of -12.5%. For the CME versus HIIT change from baseline comparison, a sample size of 12 per group provides  $>80\%$  power to detect group differences of 9.8%. For the change in OxPhos, combining HEALTH+ exercise groups (N=24, 3 dropouts/group), provides  $>80\%$  power to detect an OxPhos change of 0.039. For within exercise group (CME or HIIT) comparisons, a sample size of 12 provides  $>80\%$  power to detect an OxPhos difference of 0.055. For the CME versus HIIT change from baseline comparison, a sample size of 12 per group provides  $>80\%$  power to detect group OxPhos differences of 0.056. For the change in aim 3, combining HEALTH+ exercise groups, a sample size of N=24 (3 dropouts/ group), provides  $>80\%$  power to detect a 21%  $\dot{V}O_2$  change in HEALTH+ participants. For within exercise group (CME or HIIT) comparisons, a sample size of 12 provides  $>80\%$  power to detect 33% change in  $\dot{V}O_2$ . For the CME versus HIIT change from baseline comparison, a sample size of 12 per group provides  $>80\%$  power to detect a 30% difference in the 16-week change from baseline.

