## STUDY TIMELINE

We propose a 5-year timeline to accomplish our specific aims (**Table 1**). By conducting a rigorous, prospective, randomized clinical trial testing two exercise regimens, we will overcome limitations of previous studies investigating non-pharmacological approaches to improving the *healthspan* of people living with HIV. This design enables us to characterize the clinical (i.e., physical function and patient-reported fatigue) and translational (i.e., mitochondrial bioenergetics) effects of these interventions in an understudied, yet growing, population. To ensure that we meet enrollment and data collection milestones, we anticipate 4.5 full years of research procedures, with the remaining 6 months to finalize data analyses and disseminate the final study results.

R01 Cognitive substudy (HEALTH-COG) will leverage newly enrolled participants at the two sites of the parent HEALTH study (R01AG066562), add a University of Alabama at Birmingham (UAB) site, add new measures (psychological mechanisms of adherence, cognitive function, biomarkers) and a 12 month follow-up. This study is optional (to UCD/UW participants) and open to anyone enrolled in the parent HEALTH study. The sub-study R01 proposes to enroll/randomize 110 participants (UAB=60, University of Washington (UW)/University of Colorado Denver (UCD)=50 total between the two sites). Based on current enrollment numbers at the parent study sites (UCD=37 and UW=31), we anticipate it will be feasible for the new R01 to enroll the remaining participants across both sites (~32 participants), and due to timing of funding in relation to enrollment at UCD and UW, approximately 8-10 additional participants at both UCD and UW will need to enroll to meet and overall goal of 110 in this sub-study. The parent study end date is ~2 years into new R01 (yielding 2-3 additional years of study).

| Table 1.               |     |                      |   |
|------------------------|-----|----------------------|---|
| Timing
(Year/Month) |     | Enrollment
Target | Milestones  |
| Year 1                 | JIT |                      | 
 
Protocol & Manual of procedures finalized
 
IRB approvals
 
Hospital/research center approvals
 
Data transfer agreements between UCD-AMC and UW finalized and executed
 
  |

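### The cognitive moderation analysis names sex-by-group and race-by-group terms without time, so in stage 1 it estimates about half the moderation of the plan's own treatment effect and loses power

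*Combined protocol and SAP*

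**What the plan says.** Under Cognitive Substudy Statistical Analysis (section F, Analysis Plan), the stage 1 model covers baseline to 4 months. It is a mixed model with group, time, group-by-time and site as fixed effects and participant as a random effect. The plan states which parameter carries the answer: "The significant interaction term in above model indicates a significant difference between two trajectories/slopes, i.e., treatment effect".

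The stage 2 model covers 4 to 7 months. It has both randomised factors, exercise arm (Group1) and coaching arm (Group2), each crossed with time, and it writes the three-way Group1-by-Group2-by-time term in full.

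The moderation sentence follows as an exploratory analysis: "sex-by-group interaction and/or race-by-group interaction will be included in above models to explore the potentially moderating effects". It cites a published moderation method but gives no equation, and neither named term includes time. No SD, within-person correlation, effect size or power is stated for the cognitive outcomes or for moderation.

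**The concern.** If the treatment effect is group-by-time, a variable that modifies it enters as moderator-by-group-by-time. A moderator-by-group term added alone to a repeated-measures model is forced to be constant across visits. It asks whether the HIIT-CME gap, averaged over all visits including the pre-treatment one, differs by sex or race.

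A true sex or race difference in response would then tend to be reported at about half its size and be harder to detect, and a null result could be read as no moderation. If the rule given for stage 2, that non-significant interactions are dropped from the final model, were also applied here, the diluted estimate might not be reported at all. No primary conclusion depends on this analysis.

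**Working it through.** **Inputs**
- Treatment-effect parameter and moderation terms: Cognitive Substudy Statistical Analysis, as above.
- Sidedness: "All tests will be two sided" (same section).
- Alpha: "with a 0.05 significance level", stated in section F for Aims 1 and 2 only; assumed here, before any false discovery rate adjustment.
- Within-person correlation ρ: section F uses values "of 0.7 or 0.5 to estimate the standard deviation (SD) of the outcome change", for Aims 1 and 2. None is given for cognition, so a range is shown.
- Size: "The sub-study R01 proposes to enroll/randomize 110 participants" (Study Timeline). Applying the parent trial's 20% dropout gives 110 × 0.8 = 88 evaluable (assumption).
- Women: 25%, the parent-trial goal, carried over (assumption). Allocation 1:1.

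**The plan's own figures.** There is none on this point to reproduce. The rule used below, SD of change = SD × √(2(1−ρ)), can be checked on Aim 2: SD 180, ρ = 0.5, difference 20% of 580 = 116, 40 per arm. SD of change = 180 and SE = 180 × √(2/40) = 40.2, so z = 2.88 and power is about 82%, in line with the stated figure of more than 81%.

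**What each term estimates in stage 1.** Let d be the sex difference in the baseline-to-4-month treatment effect. Assume two complete visits, equal variance σ² at both, and correlation ρ.

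| Visit | Expected sex difference in HIIT-CME gap |
|---|---|
| Baseline | 0 (randomisation) |
| 4 months | d |

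- Sex × Group × Time estimates d − 0 = d, with per-person variance 2σ²(1−ρ).
- Sex × Group alone estimates (0 + d)/2 = d/2, with per-person variance of the two-visit mean, σ²(1+ρ)/2.

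Ratio of noncentralities, two-way to three-way: ½ × √[2(1−ρ)] ÷ √[(1+ρ)/2] = √[(1−ρ)/(1+ρ)]. This is below 1 for every positive ρ. The split by sex or race cancels, so the ratio is the same for both moderators.

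**Power of the two-way test when the three-way test has 80%** (noncentrality 2.80, normal approximation):

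| ρ | Ratio | Two-way power |
|---|---|---|
| 0.5 | 0.577 | 36.6% |
| 0.6 | 0.500 | 28.8% |
| 0.7 | 0.420 | 21.8% |
| 0.8 | 0.333 | 15.4% |
| 0.9 | 0.229 | 9.9% |

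**What the correct test can detect.** With 88 evaluable there are 11 women and 33 men per arm. At ρ = 0.7 the SE of the three-way term is √0.6 × √(2/11 + 2/33) = 0.775 × 0.492 = 0.381 SD. The difference detectable with 80% power is 2.80 × 0.381 = 1.07 SD. It is 1.38 SD at ρ = 0.5 and 0.87 SD at ρ = 0.8. For d = 0.5 SD at ρ = 0.7, power is 25.9% (three-way) against 8.5% (two-way).

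**Simulation** (88 participants, ρ = 0.7, d = 1.068 SD, 4,000 data sets). The two-way estimate averaged 0.542 with 22.4% power; the three-way estimate averaged 1.063 with 78.7%. A smaller check with fitted random-intercept models (150 data sets) gave 20% against 85%. With no moderation, the two-way test rejected in 4.8% to 5.3% of data sets across ρ of 0.5, 0.7 and 0.8.

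**Stage 2.** Let m be the moderator difference in an arm gap at 4 months and c the further difference arising by 7 months. The two-way term estimates (m + m + c)/2 = m + c/2; the three-way term estimates c.
- Coaching (Group2) is randomised after week 16, so m = 0 on average and the two-way term is again half, c/2.
- For exercise arm (Group1) the 4-month visit is already post-intervention, so m need not be zero. The two-way term mixes retained stage 1 moderation with later change.

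**The case against.** The strongest reply is that the sentence is shorthand. The section's prose uses 'group difference' for what it then tests as group-by-time, so sex-by-group could mean sex modifying that effect. The plan also contrasts mean changes between groups, and sex-by-group on change would be the right quantity. The cited moderation method might supply the missing detail.

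This makes the literal reading less than certain but does not remove the problem. The same section writes time into its interactions elsewhere, both in the stage 2 model and in the physical activity models. Nothing ties moderation to change scores, and the cited source cannot be consulted from these documents. Two analysts could fit different models from the same sentence.

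The points that stand limit the size of the concern. The two-way term is a diluted version of the right parameter with valid type I error, so it is not an invalid test. The analysis is labelled exploratory. The recommended test would also miss moderate differences at this sample size, so a reader should not infer that the correct term would find what the stated term misses.

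**Conclusion.** The concern holds in a limited form. The named terms do not match the plan's own stage 1 treatment-effect parameter. Followed literally, with two complete visits and equal variances, they estimate about half the moderation and lose power for any positive correlation: from 80% to about 37%, 22% or 10% at ρ of 0.5, 0.7 or 0.9.

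A reader might infer a single figure, such as a quarter of the available power. The documents do not support that. It needs ρ near 0.7, which section F assumes for the 400-m walk and not for cognition. With the three-way test at 80% power, the share retained runs from 46% at ρ = 0.5 to 12% at ρ = 0.9.

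A reader might also extend the half-effect result to every model. It applies to stage 1 and to moderator-by-coaching in stage 2, but not to moderator-by-exercise-arm in stage 2, where the two-way term is a mixture.

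**What to change.** Replace the moderation sentence so that it names the terms:
- **Stage 1:** sex × Group × Time and race × Group × Time, with all lower-order terms. Moderator × Group on the 4-month score, adjusted for the baseline score, targets the same quantity.
- **Stage 2:** moderator × Group1 × Time and moderator × Group2 × Time, with all lower-order terms.
- **Reporting:** the difference in change between arms within each sex and race group, and the three-way estimates, all with 95% confidence intervals and whether or not they are significant.
- **Interpretation:** keep the exploratory label and state that only large differences are detectable (about 1.07 SD for sex under the assumptions above), so that a null result is not read as evidence of no moderation.

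The cost is a short edit to the analysis plan. No new data, visits or participants are needed.
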